## 4.7. Pharmacokinetic Variables

The Pharmacokinetic (PK) variables are concentrations of functional REGN5069 in serum and time.

## 4.8. Immunogenicity Variables

The immunogenicity variables are ADA status, titer, and timepoint/visit. Serum samples for ADA will be collected at the clinic visits specified in Appendix 11.1. Samples positive in the REGN5069 ADA assay will be further characterized for ADA titers.

#### **4.9. Moticon Digital Insole Device Sub-Study for Gait Assessments**

Only study sites selected for participation in the Moticon sub-study for gait assessments using the digital insole device are to perform the Moticon-related procedures at the time points according to [Table 3](#). This sub-study is to enroll approximately 13 patients per treatment group to obtain data on at least 10 patients per treatment group for a total of approximately 30 patients across the entire sub-study.

The principal purpose of this sub-study is to assess functional mobility gait parameters as measured by the Moticon insole device in patients with pain due to OA of the knee without an analgesic treatment and in the presence of potential analgesic treatment. The study is to also examine correlations of these gait parameters with the WOMAC pain subscale score.

Moticon sub-study will be analyzed outside of this SAP. This data will be as an Appendix of the clinical study report. All listings outputs produced under this SAP, however, will contain a MOTICON participation flag.

## 5. STATISTICAL METHODS

For continuous variables, descriptive statistics include the following: the number of patients reflected in the calculation (n), mean, median, standard deviation (SD), minimum, maximum, and the first and third quartiles (Q1 and Q3).

For categorical or ordinal data, frequencies and percentages are displayed for each category.

Unless otherwise specified, table content is to be presented sorted by descending order of frequency of system organ class for the REGN5069 1000 mg group.

**Study Observation Period** – Unless otherwise stated, analysis of all safety and non-safety variables captured at multiple visits are to be analyzed by the following observations periods:

- *The Pre-Treatment Period* is defined as the time from signing the ICF to before the first dose of study drug.
- *The Treatment Period* is defined as the days from first dose of study drug to the day of last dose + 28 days (4 weeks). Summaries for the Treatment Period are based on the SAF.
- *The Follow-Up Period* is defined from the end of the Treatment Period to the Week 36 Visit/Early Termination Visit, regardless of the patient having completed the treatment period (week 12 visit) or not.
- *The Post-Follow-Up Period* is defined from the end of the Follow-Up Period to the phone call/Early Termination Visit.

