### 8.1.3. Early Termination Visit

Patients who are withdrawn from the study before the primary endpoint visit (week 12) will be asked to return to the clinic for 2 visits: once for an early termination visit consisting of the early termination assessments described in [Table 1](#) and again at the primary endpoint visit (week 12), for studies with a primary efficacy endpoint. Patients who are withdrawn from the study after the primary endpoint visit will be asked to return to the clinic for early termination assessments, only.

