### 9.4.2. Serious Adverse Events

All SAEs, regardless of assessment of causal relationship to study drug, must be reported to the sponsor (or designee) within 24 hours.

Information not available at the time of the initial report must be documented in a follow-up report. Substantiating data such as relevant hospital or medical records and diagnostic test reports may also be requested.

In the event the investigator is informed of an SAE after the patient completes the study, the following will apply:

- SAE with an onset within 30 days of the end of the follow-up period or within 226 days of last study drug administration if the patient early terminated from the study - the SAE will be reported to the sponsor. The investigator should make every effort to obtain follow-up information on the outcome until the event is considered chronic and/or stable.
- SAE with an onset day greater than 30 days from the end of the follow-up period/early termination visit - only fatal SAEs and those deemed by the investigator to be drug-related SAEs will be reported to the sponsor. The investigator should make every effort to obtain follow-up information on the outcome of a drug-related SAE until the event is considered chronic and/or stable.
- SAE reported by the patient at the end-of-study phone call and deemed by the investigator to be drug-related will be reported to the sponsor. The investigator should make every effort to obtain follow-up information on the outcome of a drug-related SAE until the event is considered chronic and/or stable.

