## 5.8. Analysis of Safety Data

The analysis of safety and tolerability is to be performed on the SAF, as defined in Section 3.2.

The safety analysis is to be based on the reported AEs and other safety information (clinical laboratory evaluations, vital signs, 12-lead ECG, Physical Examination, etc.) and is to be summarized by treatment group.

Treatment-Emergent Potential Clinically Significant Values (PCSV) in laboratory variables, vital signs and ECG are defined in Appendix 11.2.

The summary of safety results will be presented for each treatment group and by visit where applicable.

**Study observation period:** The observation period is divided into the four segments defined in Section 5.

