### 5.8.1. Adverse Events

The verbatim text, the preferred term, and the primary SOC are to be listed in patient listings. Summaries that include frequencies and proportions of patients reporting AEs are to include the preferred terms and the SOCs.

**Pre-treatment AEs** are defined as AEs that developed or worsened during the Pre-Treatment Period.

**Treatment-emergent AEs (TEAEs)** are defined as AEs that developed or worsened during the Treatment Periods.

**Follow-Up AEs** are defined as AEs that developed or worsened after treatment period end (more than 4 weeks after the last dose of study drug) but before Week 36 visit.

The focus of adverse event reporting in the clinical study report is on TEAEs.

Summaries of TEAEs by treatment group, summarizing number (percentage) of patients within the specified category, during the study and by study period as applicable include:

- Overview of TEAEs, summarizing number of events,
  - Total number of TEAEs
  - Total number of Serious TEAEs
  - Patients with any TEAEs
  - Patients with any Serious TEAEs
  - Patients with any TEAEs leading to death
  - Patients with any TEAEs leading to withdrawal from study
  - Patients with any TEAEs leading to permanent study treatment discontinuation
- All TEAEs by SOC and PT
- All TEAEs by SOC, PT, severity

- All TEAEs by SOC, PT, relationship
- Study drug related TEAEs by SOC and PT
- TEAEs resulting in permanent study drug discontinuation by SOC and PT
- TEAEs leading to study drug infusion interruption by SOC and PT
- Serious TEAEs by SOC and PT
- All AEs by SOC and PT
- All AEs by severity
- All SAEs, by study period
- All SAEs by severity and study period
- All SAEs by relationship, treatment and follow-up period

Follow-up AEs will be summarized similarly as TEAEs, as well as AEs occurring during Treatment and Follow-up Periods combined.

Listing to include:

- Listing of AEs leading to death
- Listing of TEAEs leading to permanent study treatment discontinuation
- Listing of TEAEs leading to infusion interruption
- Listing of TEAEs leading to withdrawal from study
- Listing of patients with Serious TEAEs
- Listing of all joint replacements

Counts are to be provided according to treatment group and combined REGN5069 group for each PT within each primary SOC. Percentages are to be calculated based on the SAF in each treatment group and sorted by descending order of frequency of system organ class for the REGN5069 1000 mg group.

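### For early terminators, SAP 5 leaves events after both the early-termination visit and last dose + 28 days in no observation period, while SAP 5.8.1 ends follow-up at a Week 36 visit they may not have

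*SAP*

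**What the plan says.** SAP Section 5 sets four observation periods. The Treatment Period runs from first dose to last dose + 28 days and is not cut short by early termination. The Follow-Up Period "is defined from the end of the Treatment Period to the Week 36 Visit/Early Termination Visit". The Post-Follow-Up Period "is defined from the end of the Follow-Up Period to the phone call/Early Termination Visit". The periods are introduced with a carve-out: "Unless otherwise stated, analysis of all safety and non-safety variables captured at multiple visits are to be analyzed by the following observations periods".

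SAP 5.8 carries these periods into the safety analysis: "The observation period is divided into the four segments defined in Section 5". SAP 5.8.1 then gives its own definition of follow-up AEs, as those that developed or worsened "after treatment period end (more than 4 weeks after the last dose of study drug) but before Week 36 visit". It does not mention the ET visit or patients who never reach Week 36. The same section plans SAE tables by study period, by severity and period, and by relationship and period. It also plans follow-up AE summaries and summaries for the treatment and follow-up periods combined.

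On collection, Protocol 9.4.2 makes an SAE reportable if its onset is "within 226 days of last study drug administration if the patient early terminated from the study"; SAP 4.5.1 repeats this. Protocol 8.1.3 asks patients withdrawn before Week 12 to attend an ET visit and then return at Week 12. In Protocol Table 1 the ET visit shares a column with the joint-replacement pre-operative visit. Protocol Table 2 continues AE collection with visits 4 and 20 weeks after surgery.

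**The concern.** For an early terminator, Section 5 ends follow-up at the ET visit and gives Post-Follow-Up no length. If the ET visit is within 28 days of the last dose, the Follow-Up Period ends before it begins. Yet the protocol foresees information arriving after that visit: reportable SAEs, the Week 12 return visit, and the visits after joint replacement.

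Two programmers following this SAP could therefore produce different counts. One applying Section 5 has no period for such an event, so it drops out of every table split by period. One applying 5.8.1 with Week 36 taken as a calendar target counts it as a follow-up event. The patients concerned are those who left early. Where the combined ET/pre-operative visit counts as the ET visit, the unassigned events include the surgery itself and its post-operative complications, and joint safety is the concern that Protocol 3.2.1 gives for its intensive monitoring.

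**Working it through.** **Inputs.** Doses on Days 1, 29 and 57 (Protocol Figure 1 note and Table 1). Week 12 is Day 85 and Week 36 is Day 253 (Protocol Table 1). Treatment Period ends at last dose + 28 (SAP 5). SAE window for early terminators ends at last dose + 226 (Protocol 9.4.2, SAP 4.5.1).

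**The plan's own figure.** Week 36 target day, less last planned dose day, plus the 30 days used for completers: 253 − 57 + 30 = 226. This matches exactly.

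**Days in no Section 5 period.** Let L be the day of last dose and E the day of the ET visit. An event is unassigned only if it starts after both the Treatment Period and the ET visit:

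unassigned days = (L + 226) − max(L + 28, E)

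- E on or before L + 28: 226 − 28 = 198 days, whatever the number of doses (198/226 = 88%).
- E = L + 42: 226 − 42 = 184 days.
- E = Day 120: (L + 226) − 120.

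| Doses | L | L + 28 | L + 226 | Unassigned, E ≤ L + 28 | Unassigned, E = Day 120 |
|---|---|---|---|---|---|
| 1 | 1 | 29 | 227 | 198 | 107 |
| 2 | 29 | 57 | 255 | 198 | 135 |
| 3 | 57 | 85 | 283 | 198 | 163 |

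Events after the ET visit but within 28 days of the last dose are not unassigned. With E = L + 14, the next 14 days are still in the Treatment Period; the 198 days follow.

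**What SAP 5.8.1 would recover.** If its Week 36 limit is read as Day 253, it covers days L + 29 to 252. Of the 198 days, that is 198, 195 or 167 after one, two or three doses. It leaves 0, 3 or 31 days (Day 253 to Day 227, 255 or 283; none in the first case).

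**Week 12 return visit.** After three on-schedule doses, 57 + 28 = 85, so a return on the Week 12 target day is still in the Treatment Period. After one dose it is 85 − 29 = 56 days past that period; after two, 85 − 57 = 28 days past.

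**The case against.** The strongest reply is the carve-out in Section 5. Its periods yield where another section states otherwise, and 5.8.1 does state an AE-specific rule with no ET cut-off. On that reading most of the gap closes. This has force but does not settle the matter. SAP 5.8, which contains 5.8.1, expressly adopts the Section 5 segments. The SAE tables are specified by study period. And 5.8.1 gives no end date for a patient with no Week 36 visit, so reading it as Day 253 is an inference.

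A reader might infer that every AE and SAE after early termination is lost. The documents do not support that:

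- Events within 28 days of the last dose stay treatment-emergent, whether or not the patient has terminated.
- The tables of all AEs in 5.8.1, and the listing of AEs leading to death, state no period limit and would still show the events.
- Non-serious AEs are collected only to the last study visit (Protocol 9.4.6), so that part is narrow. It arises mainly through the Week 12 return after one or two doses, or the visits after joint replacement.

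A reader might also try to put a number on the missing SAEs from the assumed 15% dropout (0.15 × 240 = 36 patients). That does not work. The documents give no SAE rate. The 15% is a sample-size assumption. Not every dropout would have the maximum gap. Reporting after a patient leaves depends on the investigator being informed. The next item in Protocol 9.4.2 also limits reports of SAEs starting more than 30 days after the ET visit to fatal or drug-related ones, which overlaps awkwardly with the 226-day item. A difference in loss between arms is possible but hypothetical.

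**Conclusion.** The point holds in limited form. SAP 5 and 5.8.1 give different ends of follow-up for patients who terminate early, and neither assigns every reportable event. Under Section 5, up to 198 of the 226 SAE reporting days lie in no period, fewer when the ET visit comes later than last dose + 28. Under 5.8.1, with Week 36 assumed to mean Day 253, at most 31 days are left over.

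The consequence is misclassification in the by-period SAE tables, the follow-up AE tables and the combined treatment plus follow-up tables. No treatment-emergent count, efficacy result or output without a period limit changes. Joint-replacement events are affected only if the combined pre-operative visit is treated as the ET visit. SAP 1.2.4.2 reports a joint replacement in a single patient, and the documents do not say when it took place. The day counts assume on-schedule dosing and target visit days. No reliable expected number of events can be given.

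**What to change.** Use one definition in SAP 5 and have 5.8.1 refer to it. For AE and SAE classification:

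- **Follow-Up Period:** from the day after last dose + 28 days to the Week 36 visit, or to target Day 253 if there is no Week 36 visit, regardless of the ET visit date. State whether the end day itself is included, since 5.8.1 now stops before the visit.
- **Post-Follow-Up Period:** any AE or SAE reported with a later onset. It ends at the latest of the phone call, the last study contact and, for early terminators, last dose + 226 days.

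This keeps the Follow-Up Period of early terminators the same nominal length as that of completers. Running it to last dose + 226 instead would take a three-dose early terminator to Day 283, against about Day 253 for a completer. It also matches SAP 4.3, which already takes follow-up concomitant medications to Week 36 with no ET limit.

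The cost is a few sentences in the SAP and one date derivation, with no new data. The downside is that, for early terminators, part of the period is covered only by SAEs of which the investigator happens to be informed. A footnote to the affected tables should say so.

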### 5.1. Demographics and Baseline Characteristics

Demographic and baseline characteristics are to be descriptively summarized by treatment group, combined REGN5069, and overall based on the FAS. Parameters to be summarized include those described in Section 4.1.

### 5.2. Medical History

Medical history is to be descriptively summarized by treatment group, combined REGN5069 and overall for the FAS. Summaries are to show patient counts (percentages) by primary SOC and PT. The tables are to be sorted by descending order of frequency of system organ class for the REGN5069 1000 mg group. Within each primary SOC, PTs are to be sorted by descending order of frequency of system organ class for the REGN5069 1000 mg group.

### 5.3. Prior / Concomitant Medications

The analysis population is based on the SAF.

#### Prior Medications

All prior medications, dictionary coded by WHO, are to be descriptively summarized by treatment group, and combined REGN5069 based on the FAS. Summaries are to present patient counts (and percentages) for all prior medications, by descending order of frequency of ATC followed by ATC level 2, ATC level 4 and preferred term for the REGN5069 1000 mg group. In case of equal frequency across anatomic or therapeutic categories, alphabetical order is to be

used. Patients will be counted once in each ATC category (anatomic or therapeutic) linked to the medication but may be counted several times for the same medication.

#### Concomitant Medications

All concomitant medications, dictionary coded by WHO, are to be descriptively summarized by treatment group, and combined REGN5069 based on the SAF. Summaries are to present patient counts (and percentages) for the concomitant medication groups described in Section 4.3 for all concomitant medications, by descending order of frequency of ATC level 2, followed by ATC level 4 and preferred term. In case of equal frequency across anatomic or therapeutic categories, alphabetical order is to be used. Patients are to be counted once in each ATC category (anatomic or therapeutic) linked to the medication, hence may be counted several times for the same medication.

When medication start/end date is missing, the rules for determining whether a medication is prior, concomitant, or post-treatment, are specified in Section 6.3.

#### Rescue Medication

The number (percentage) of patients using rescue medication during the Treatment Period are to be summarized by treatment group and overall based on the SAF. Analogous analyses are to be performed for the Follow-up Period, up to Week 24 visit. Rescue medication inadvertently collected in the diary past Week 24 (e.g. due to missing visits because of COVID-19 pandemic) will be censored and not included in the outputs.

For patients taking rescue medication, usage of rescue medications (measured in mg) is summarized by study week.

Descriptive statistics of the weekly average usage of rescue medications are to be presented by treatment group based on the SAF.

### **5.4. Prohibited Medications**

The analysis population is based on the SAF.

The number (percentage) of patients with prohibited medications are to be descriptively summarized by treatment group, and combined REGN5069 based on the SAF. The tables are to be sorted by decreasing frequency of ATC Level 2, ATC Level 4, and preferred term in the REGN5069 1000 mg group.

### **5.5. Patient Disposition**

The analysis population is based on the FAS.

The end of study is defined as the date when the last patient completes the last phone call, withdraws from the study, or is lost to follow up (ie, the patient can no longer be contacted by the investigator).

Dose modification for an individual patient is not allowed.

Patients who permanently discontinue from study drug and who do not withdraw from the study are asked to return to the clinic for all remaining study visits and to participate in all study phone calls per the visit schedule.

Patients who permanently discontinue from study drug and who opt to withdraw from the study are asked to complete study assessments as follows:

- Patients who are withdrawn from the study before the primary endpoint visit (week 12) are asked to return to the clinic for 2 visits: once for an early termination visit consisting of the early termination assessments described in [Table 3](#) and again at the primary endpoint visit (week 12).
- Patients who are withdrawn from the study after the primary endpoint visit are asked to return to the clinic for early termination assessments, only.

The disposition of patients in the study are to be summarized by treatment group, combined REGN5069 and overall for FAS.

Percentages are to be calculated using the number of screened patients as the denominator for:

- Screened patients (defined as having signed the ICF).
- Screen Fail patients. Reason for screen failure is to be provided.
- Patients treated but not randomized (if applicable)
- Patients randomized (defined as having received a randomization number per IWRS). This row is to reflect grouping based on randomization assignment.
- Patients did not meet inclusion/exclusion criteria but randomized (if applicable).

Percentages are to be calculated using the number of randomized patients as the denominator for:

- Patients randomized but not treated. This row is to reflect grouping based on randomization assignment.
- Patients randomized and treated.
- Patients treated differently than randomized. This row is to reflect grouping based on randomization assignment.
- Patients who completed study treatment, patients who discontinued treatment
- Patients who completed study treatment period (defined as completing Week 12 visit), patients who discontinued study treatment period and reason for study treatment period discontinuation, patients who had infusion interruptions and reason.
- Patients who completed study follow-up period (defined as completing Week 36 visit).
- Patients who completed the study (defined as having completed Week 52 phone call), patients who withdrew from the study and reason for study withdrawal.

In addition, a summary of the impact of COVID-19, with all information described in Section 9, will be provided.

Summary of the number (percentage) of patients in each analysis set are to be by treatment group, combined REGN5069, and overall.

Additionally, the following listings are to be provided (if applicable):

- Listing of patients treated but not randomized, patients randomized but not treated, patients randomized but not treated with the randomized treatment, patient disposition for all randomized patients, and patients prematurely discontinued from treatment, with reasons.
- Listing of screening failures and reasons for all screen-failed patients.

## **5.6. Extent of Study Treatment Exposure and Compliance**

The analysis population is based on the SAF.

### **5.6.1. Exposure to Investigational Product**

The treatment exposure to REGN5069 and placebo doses is calculated as:

- (Date of last administration of study drug - date of the first study drug administration after randomization) + 28

The duration of exposure are to be summarized for each treatment group using the number of patients (n), mean, standard deviation, median, Q1, Q3, minimum, and maximum.

The number (percentage) of patients with exposure duration periods are to be presented by specific time periods. The time periods of interest are specified as:  $\geq 1$  day,  $\geq 4$  weeks,  $\geq 8$  weeks.

The length of the study observation period (days) are to be calculated as:

- (Date of last study Visit [up to End of Follow-up Clinic Visit] – date of first study drug dose) +1.

The length of the total study participation period (days) will be calculated as:

- (Date of last study Visit or last Phone call - date of first study drug dose) +1

The study observation duration is to be summarized for each treatment group using the number of patients (n), mean, standard deviation, median, Q1, Q3, minimum, and maximum.

The number (percentage) of patients with observation periods is to be presented by specific time periods. The time periods of interest are specified as:  $\geq 1$  day,  $\geq 29$  days,  $\geq 57$  days,  $\geq 85$  days,  $\geq 113$  days,  $\geq 141$  days,  $\geq 169$  days,  $\geq 197$  days,  $\geq 225$  days,  $\geq 253$  days,  $\geq 365$  days

